6.1. General statistical methodology

The database system for both inclusion procedures and follow-up is REDCap (www.project-redcap.org), and the instruments have been developed by the Institute of Hygiene and Tropical Medicine at NOVA University.

Data entry for both inclusion and follow-up procedures is conducted online using the browser version, which means that no participant data is stored locally and that the study responsible(s) can monitor the data collection in real-time.

The randomization code was developed by the trial statistician, [name]. This code produces an allocation table for all the stratification layers and all the sites, with block sizes varying randomly between 4 and 6 within each individual stratum. The allocation table used for the study has not been seen and is not available to any of the researchers involved in the study and it was implemented by an independent statistician, [name], in Bissau.

From the databases of the trials in Guinea-Bissau and Mozambique, their analysis will be performed by either STATA version 17 software (Stata, College Station, TX) or SPSS version 26.

The combined data analysis will begin when the last participant in the multicentric RCT has completed the follow-up period or after the 182 day of the study and data has been cleaned.

Descriptive statistical techniques (absolute and relative frequency distribution) will be used to analyze the quality of the database through the evaluation of two aspects: completeness (field filling) and consistency (consistency between the categories marked in two related fields). The completeness indicator will be calculated as the proportion of filled fields in relation to the total of records, in percentage. Regarding completeness, the results will be categorized as the percentage of records without filling out as follows: excellent (<10% of records without filling out), regular (11 to 30%) and low (>30% of records without filling out).

Primarily a descriptive analysis will be performed of all information contained in the two study groups (BCG and placebo). All variables will be analysed, one by one, to know their distribution. Background factors will be summarised by counts (percentages), means (standard deviation) or medians (interquartile range) as appropriate. Proportions will be compared using the chi-square test - χ^2 test or Fisher's Exact test (categorical variable) or Student's t-test or Mann-Whitney test (quantitative variable) according to the distribution of variables. Statistical significance was set at the 5% level (two-tailed tests) and 95% confidence intervals (95%CI) for the estimates.

The endpoints variables (table 1) will be analyzed using univariate analysis (Logrank test) and Multivariate analysis (Cox Proportional Hazard Regression, or Cox Regression), stratified by the block randomization variables gender (male/female) and occupational group (doctors/ nurses/other) in addition to site. Covariates will be tested in the model univariate, and only those that were associated with the outcome at a significance level of at least 20% will be retained in a possible multivariate model. A significance level (p-value) of less than 0.05 and its respective confidence intervals (CI) will be used.

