Data will be reported quantitatively. All analyses will be performed from the intention-to-treat principle. Missing data on background variables will be dealt with by multiple imputation. Final data analysis will begin when the last participant in the multicentric RCT has completed the follow-up period. The primary endpoint, work absenteeism due to illness, will be reported as the total number of sick days with standard deviation. Total days of absenteeism will be analysed using a Bayesian negative binomial regression with a fixed effect for BCG, hospital, professional category, age, enrolment week and number of average workdays per week. The brm function from the R package "brms" will be used for fitting the negative binomial model. The effect will be reported as a relative risk with 95% confidence interval (CI). Please refer to section interim analysis for type-1 error control and power.

Similar regression models will be used for secondary endpoints. Cumulative incidence outcomes will primarily be analysed using Cox Proportional Hazard Regression.

Continuous baseline characteristics will be reported as means with the standard deviation or medians with the inter-quartile range, as appropriate. Categorical baseline characteristics will be reported as count and percentage. No statistical testing for baseline characteristics will be reported.

Please refer to the Data Analysis Plan for more details.

Interim analysis

Every month, an interim analysis will be conducted for each study site and of the combined dataset. Interim analyses will start after the 200th participant has been recruited across the two sites. The primary endpoint will be analysed as described above. The Bayesian model yields a posterior distribution of the relative risk (RR). The posterior probability of the superiority hypothesis ($RR < 1$) will be calculated. If during any of the interim analyses, the posterior probability of superiority is > 0.995 , a conclusion is reached, and the trial will be stopped.

Monthly, the following secondary endpoints will be reported from the sites: hospital admissions, and deaths.

IMPLEMENTATION

Inception

The study will begin with an inception meeting to be held in Cape Verde or virtually, depending on travel and quarantine recommendations at the time. Besides administrative issues, the meeting will address:

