Data will be reported quantitatively. All analyses will be performed from the intention-to-treat principle. Missing data on background variables will be dealt with by multiple imputation. Final data analysis will begin when the last participant in the multicentric RCT has completed the follow-up period. The primary endpoint, work absenteeism due to illness, will be reported as the total number of sick days with standard deviation. Continuous baseline characteristics will be reported as means with the standard deviation or medians with the inter-quartile range, as appropriate. Categorical baseline characteristics will be reported as count and percentage. Statistical testing for baseline characteristics will be performed. Days of absenteeism will be analysed using a Bayesian negative binomial regression with a fixed effect for BCG, hospital, professional category, age, enrolment week and number of average workdays per week. Incidence data will be analysed in Cox proportional hazards models. Monthly, data on absenteeism by randomization group will be reported to the DSMB.

Trial registration

The trial is registered at clinicaltrials.gov. (<https://clinicaltrials.gov/ct2/show/NCT04641858>)

Funding

EDCTP is funding the run-in costs for the BCG-COVID-RCT, including trials in the respective countries and for training and management.

Study management, monitoring and quality control

The project is led by an International Steering Committee (ISC) consisting of PIs in each of the five countries involved: [name] (international coordinator), PI from Denmark; [name], PI from Guinea-Bissau; [name], PI from Portugal; [name], PI from Cape Verde; and [name], PI from Mozambique. The overall coordination is the responsibility of the Danish partner. The leader has extensive leadership experience from running a Center of Excellence in Denmark and the research group of the Bandim Health Project in Bissau for many years. The Bandim Health Project has a history of past collaboration with the Portuguese partner. The research group will hold teleconferences at least once a week with a formal pre-established agenda on training, enrollment, follow-up, losses to follow-up, staff turnover, vaccine logistics, quality control of data collection, data entry and database management, interim analysis, communication and dissemination activities, other risks. Decisions from each meeting are recorded by the coordinator.

2. Definitions

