Absenteeism besides COVID-19	Refers to the number of days absent from work due to illness besides COVID-19	Quantitative	Numeric	In days
Absenteeism for infections	Refers to the number of days (unplanned) absent from work due to infections	Quantitative	Numeric	In days
Absenteeism for respiratory infections	Refers to the number of days (unplanned) absent from work due to respiratory infections	Quantitative	Numeric	In days
COVID-19 infection	Describes if the participant is positive for SARS-CoV2 or has had COVID-19	Qualitative	Nominal	No Yes
Death	Whether the participant died during follow-up	Qualitative	Nominal	No Yes
Cumulative incidence of infectious disease episodes	Cumulative incidence of infectious disease episodes	Quantitative	Numeric	Episodes
Cumulative incidence of respiratory infectious disease episodes	Cumulative incidence of respiratory infectious disease episodes	Quantitative	Numeric	Episodes
Cumulative incidence of hospital admissions	Cumulative incidence of hospital admissions	Quantitative	Numeric	Admissions
Cumulative incidence of infectious disease hospital admissions	Cumulative incidence of infectious hospital admissions	Quantitative	Numeric	Admissions

Variable	Definition	Type	Scale	Domain
Cumulative incidence of respiratory infectious hospital admissions	Cumulative incidence of respiratory infectious hospital admissions	Quantitative	Numeric	Admissions
Cumulative incidence of hospital admissions due to documented COVID-19	Cumulative incidence of hospital admissions due to documented COVID-19	Quantitative	Numeric	Admissions
Cumulative incidence all-cause and infectious intensive care admission	Cumulative incidence all-cause and infectious intensive care admission	Quantitative	Numeric	Nights
Cumulative incidence of intensive care admission due to documented COVID-19 infection	Cumulative incidence all-cause and infectious intensive care admission	Quantitative	Numeric	Nights

6. General Statistical considerations

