6.4. Inferential statistics

The comparison between the intervention versus placebo groups will be done using the chi-square test (χ^2 test or Fisher's Exact test (categorical variable) or Student's t-test or Mann-Whitney test (quantitative variable) according to the distribution of variables.

Fisher's test is useful for categorical data, which result from classifying objects in two different ways and when considering the sample number low; it is used to examine the significance of the association (contingency) between the two types of classification. It is used because the approximation is inadequate when the sample size is small, or if the data are very unevenly distributed among the cells of the table, resulting in the cell count predicted by the null hypothesis (the "expected values") being low. Although considered conservative, we can - for its use - use the usual rule for deciding whether the chi-square approximation test is good enough, where the chi-square test is not appropriate when the expected values in the cells of the contingency table are below 5, or below 10 when there is only one degree of freedom. In fact, for small, sparse, or unbalanced data, the exact and asymptotic p-value can be very different and can lead to opposite conclusions about the hypothesis of interest. Fisher's exact test keeps the row and column totals fixed, and can therefore be used regardless of the sample characteristics. It becomes difficult to calculate with large samples or well-balanced tables; under these conditions, the χ^2 test is appropriate.

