When you have a small sample and the numerical variable is not known to have a normal distribution (or cannot be verified satisfactorily), or when there is no homogeneity of variances, Student's t-test is not appropriate. In this situation, the nonparametric Mann-Whitney test (Wilcoxon rank-sum test, U-test) can be used. Unlike the t-test, which tests for equality of means, the Mann-Whitney test tests for equality of medians. The U values calculated by the test assess the degree of intermingling of the data of the two groups after sorting. The greater separation of the data together indicates that the samples are distinct, rejecting the hypothesis of equality of the medians. Total days of absenteeism will be analyzed using a Bayesian negative binomial regression with a fixed effect for BCG, hospital, professional category, age, enrolment week and number of average workdays per week. The excess absence of the event of interest can lead to data overdispersion (a phenomenon that occurs when the variance of the response variable is greater than the value of the mean). To check the overdispersion of the data we will use the deviance, which is also a statistic used to check the goodness of fit of the model.

The Kaplan-Meier method consists of dividing the follow-up time into intervals, whose limits correspond to the follow-up time when events occurred. The measure of association used in survival analysis to

compare groups is the Hazard Ratio (HR), with similar meaning to Relative Risk; HR is the probability that some participant who did not have the outcome event by a certain time, will have it at that time. HR therefore compares the instantaneous incidence with which events occur in the different groups (BCG and Placebo).

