For the univariate analysis to check the difference between the BCG versus Placebo groups we will use the Logrank test of significance by means of its p-value or confidence interval. For the univariate analysis to check the difference between the BCG versus Placebo groups we will use the Logrank test of significance by means of its p-value or confidence interval. In the multivariate analysis for the comparison of the two analyzed groups, we will use the Cox Proportional Hazard Regression, or Cox Regression. This allows us to obtain results adjusted for possible confounding variables. Cumulative incidence data will be analysed in Cox proportional hazards models. The Cox Model, which is semi-parametric, assumes that failure rates are proportional, that is, the risk of failure of the variables is constant over time. Survival analysis will allow us to correctly assess the rate at which events (outcomes) are occurring in the different groups in our study.

7. Demographics and other baseline characteristics

Baseline characteristics

Table 2 – Baseline characteristics of the participants

Variable	Type	BCG vaccine	Placebo	Statistical (P-value)
Age (years)	Quantitative	$\bar{X} \pm SD$ or Md (IQR)	$\bar{X} \pm SD$ or Md (IQR)	Student's t-test or Mann-Whitney test
Gender				
Female	Categorical	% (n/N)	% (n/N)	χ^2 test or Fisher's exact test (P-value)
Male		% (n/N)	% (n/N)	
Number adults (> 18 years) living in the household	Quantitative	$\bar{X} \pm SD$ or Md (IQR)	$\bar{X} \pm SD$ or Md (IQR)	Student's t-test or Mann-Whitney test
Adult living at home and also healthcare worker	Quantitative	$\bar{X} \pm SD$ or Md (IQR)	$\bar{X} \pm SD$ or Md (IQR)	Student's t-test or Mann-Whitney test
Number children (<18 years) living in the household	Quantitative	$\bar{X} \pm SD$ or Md (IQR)	$\bar{X} \pm SD$ or Md (IQR)	Student's t-test or Mann-Whitney test
Age of the youngest child living in the household (years)	Quantitative	$\bar{X} \pm SD$ or Md (IQR)	$\bar{X} \pm SD$ or Md (IQR)	Student's t-test or Mann-Whitney test
Animals living in the household				
Dogs	Categorical	% (n/N)	% (n/N)	χ^2 test or Fisher's exact test (P-value)
Cats		% (n/N)	% (n/N)	
Pigs		% (n/N)	% (n/N)	

Variable	Type	BCG vaccine	Placebo	Statistical (P-value)	
Birds		% (n/N)	% (n/N)		
Sheep		% (n/N)	% (n/N)		
Other		% (n/N)	% (n/N)		
Person living in the household diagnosed with COVID-19					
No	Categorical	% (n/N)	% (n/N)	χ^2 test or Fisher's exact test (P-value)	
Yes		% (n/N)	% (n/N)		
Occupation					

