Suspected but not confirmed				
No		% (n/N)	% (n/N)	χ^2 test or Fisher's exact test (P-value)
Yes	Categorical	% (n/N)	% (n/N)	
COVID test in the last 2 weeks				
No		% (n/N)	% (n/N)	χ^2 test or Fisher's exact test (P-value)
Yes	Categorical	% (n/N)	% (n/N)	
COVID test type				
RT-PCR (swab in the throat or nose)		% (n/N)	% (n/N)	χ^2 test or Fisher's exact test (P-value)
Rapid test for the antibodies detection in the blood (finger prick)		% (n/N)	% (n/N)	
	Categorical			
RT-PCR result				
Positive		% (n/N)	% (n/N)	χ^2 test or Fisher's exact test (P-value)
Negative		% (n/N)	% (n/N)	
Missing		% (n/N)	% (n/N)	
Rapid test result				
Positive		% (n/N)	% (n/N)	χ^2 test or Fisher's exact test (P-value)
Negative		% (n/N)	% (n/N)	
Missing		% (n/N)	% (n/N)	

8. Analysis of endpoints

Table 4 – Analysis of endpoints from Bayesian analysis

Endpoint Variable	BCG	Placebo	Risk Ratio (95%CI) p-value
Absenteeism	$\bar{X} \pm SD$ or Md (IQR)	$\bar{X} \pm SD$ or Md (IQR)	RR (95%CI) p-Value
Absenteeism for COVID-19	$\bar{X} \pm SD$ or Md (IQR)	$\bar{X} \pm SD$ or Md (IQR)	RR (95%CI) p-Value
Absenteeism besides COVID-19	$\bar{X} \pm SD$ or Md (IQR)	$\bar{X} \pm SD$ or Md (IQR)	RR (95%CI) p-Value
Absenteeism for infections	$\bar{X} \pm SD$ or Md (IQR)	$\bar{X} \pm SD$ or Md (IQR)	RR (95%CI) p-Value
Absenteeism for respiratory infections	$\bar{X} \pm SD$ or Md (IQR)	$\bar{X} \pm SD$ or Md (IQR)	RR (95%CI) p-Value

Table 5 – Analysis of endpoints from Cox regression and Poisson regression

Endpoint Variable	BCG	Placebo	Hazard Ratio (95%CI) p-value
Cumulative incidence of infectious disease episodes	rate (events / risk time)	rate (events / risk time)	HR (95%CI) p-Value
Cumulative incidence of respiratory infectious disease episodes	rate (events / risk time)	rate (events / risk time)	HR (95%CI) p-Value
Cumulative incidence of hospital admissions	rate (events / risk time)	rate (events / risk time)	HR (95%CI) p-Value
Cumulative incidence of infectious disease hospital admissions	rate (events / risk time)	rate (events / risk time)	HR (95%CI) p-Value
Cumulative incidence of respiratory infectious hospital admissions	rate (events / risk time)	rate (events / risk time)	HR (95%CI) p-Value
Cumulative incidence of hospital admissions due to documented COVID-19	rate (events / risk time)	rate (events / risk time)	HR (95%CI) p-Value
Cumulative incidence all-cause and infectious intensive care admission	rate (events / risk time)	rate (events / risk time)	HR (95%CI) p-Value

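### The primary negative binomial model omits sex, a randomisation stratum, and SAP 6.1 as worded sends seven endpoints, including the primary, to log-rank/Cox against Tables 4 and 5

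*SAP*

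**What the plan says.** Randomisation in both documents is stratified by sex and by occupational group (Protocol, Randomization; SAP, Randomization).

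For the primary endpoint, SAP 6.4 states: "Total days of absenteeism will be analyzed using a Bayesian negative binomial regression with a fixed effect for BCG, hospital, professional category, age, enrolment week". The list closes with average workdays per week. The same list stands in SAP, Statistical analysis, and in Protocol, Statistical methods. Sex is in none of the three. The Protocol abstract gives a different list, with observation week in place of enrolment week and without age. The interim rule uses the same model: "The primary endpoint will be analysed as described above. The Bayesian model yields a posterior distribution of the relative risk (RR".

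The other analyses do account for sex. SAP 6.1 stratifies the Cox analysis by sex, occupational group and site. The footnote to SAP Table 5 puts country, profession and sex in the Poisson model.

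On which endpoint gets which method, SAP 6.1 says: "The endpoints variables (table 1) will be analyzed using univariate analysis (Logrank test) and Multivariate analysis (Cox Proportional Hazard Regression, or Cox Regression". The same paragraph keeps only covariates that are associated with the outcome at the 20% level in univariate testing. Elsewhere Cox is confined to incidence endpoints: "Incidence data will be analysed in Cox proportional hazards models" (SAP, Statistical analysis) and "Cumulative incidence data will be analysed in Cox proportional hazards models" (SAP 6.4). Table 4, which holds the five absenteeism rows, is titled "Analysis of endpoints from Bayesian analysis".

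**The concern.** Two things look wrong.

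(a) A factor used to stratify the allocation would normally be in the primary model. Stratification balances the arms on sex. If sex predicts absence and the model ignores it, the model-based standard error does not credit that balance, and between-sex variation stays in the error term. The other stratum is present as professional category, and site as hospital, so sex is the only gap. No reason is given for it.

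(b) Someone who follows 6.1 to the letter would put a count of days into a log-rank test and a Cox model. The plan defines no event time for such a count, so one would have to be invented for the primary endpoint. The screening rule would also replace the fixed covariate list with one chosen from the data. The Protocol refers to the analysis plan for detail, so the wording of the SAP matters.

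**Working it through.** **Row-by-row comparison for (b).** SAP Table 1 has 15 rows.

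| Table 1 rows | Rows | SAP 6.1 | SAP Tables 4 and 5 | Same method? |
|---|---|---|---|---|
| Absenteeism day counts, including the primary | 5 | log-rank/Cox | Bayesian model, risk ratio (Table 4) | no |
| COVID-19 infection; death | 2 | log-rank/Cox | robust Poisson, risk ratio (Table 5 footnote) | no |
| Cumulative incidences | 8 | log-rank/Cox | Cox, hazard ratio (Table 5) | yes |

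So 5 + 2 = 7 rows conflict and 15 − 7 = 8 agree. A separate mismatch affects two of the eight. Both intensive-care rows, for example "Cumulative incidence of intensive care admission due to documented COVID-19 infection", are scaled in nights in Table 1, whereas Table 5 reports events per risk time with a hazard ratio. That is Table 1 against Table 5, not a conflict with 6.1.

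No power figure is attached to log-rank/Cox on absenteeism days, because the plan gives no event time from which to compute one.

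**Size of (a).** The plan has no figure of its own on this point to reproduce.

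Inputs from the documents:
- 1050 randomised 1:1 with 5% loss: 1050 × 0.95 / 2 = 498.75, taken as 499 per arm (998 in all).
- Control mean 5 days and SD 5; mean ratio 0.8; two-sided 5% level.

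Assumptions:
- Negative binomial data, variance = mean + a × mean².
- Sex rate ratio 1.25 or 2, and the sex split as shown below.
- Occupation shares 0.2/0.4/0.4, with occupation in both models.
- A maximum-likelihood negative binomial fit as a stand-in for the Bayesian model with weak priors.

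Why the standard error moves: with sex ignored, a = (25 − 5)/25 = 0.80. With a 50:50 split and ratio 2, the control means are 3.33 and 6.67, the between-sex variance is 1.667² = 2.78, and the mean of the squared means is 25 + 2.78 = 27.78. Holding the overall SD at 5, the within-sex dispersion is a = (25 − 5 − 2.78)/27.78 = 0.62. Leaving sex out folds the difference into the error term.

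Simulated ratio of the reported standard error, with sex over without sex (1,500 trials per scenario, overall SD held at 5):

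| Scenario | Sex ratio 1.25 | Sex ratio 2 |
|---|---|---|
| 50:50, no overlap with occupation | 0.994 | 0.942 |
| 50:50, occupation explains 21% of the variation in sex | 0.995 | 0.953 |
| 50:50, occupation explains 43% | 0.996 | 0.963 |
| 80% in the higher-absence sex | 0.996 | 0.971 |

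The reductions run from 1 − 0.996 = 0.4% to 1 − 0.942 = 5.8%.

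Power for a 20% reduction, 50:50 split, without and then with sex:
- Overall SD held at 5: 93.5% and 93.5% at ratio 1.25 (no gain); 95.4% and 97.1% at ratio 2 (1.7 points).
- Within-sex dispersion held at 0.8, ratio 2: 89.2% and 93.0% in one run of 1,000 trials (3.8 points), and 89.9% and 92.6% in another (2.7 points).

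The gain is therefore roughly 0 to 4 points, depending on which quantity is held fixed.

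Rejection rate with no BCG effect (10,000 trials, 50:50, no overlap): without sex 5.1% at ratio 1.25 and 4.2% at ratio 2; with sex 5.1% and 5.0%. The omission is neutral to mildly conservative.

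**The case against.** The strongest reply is that the plan already answers (b). The Protocol's analysis and interim sections, SAP Statistical analysis, SAP 6.4 and Table 4 all give absenteeism days to the Bayesian model. Two SAP passages limit Cox to incidence data, and the absenteeism table has no hazard-ratio column. An analyst filling in the tables would not invent an event time. This stands. A reader might infer that the plan has a rival Cox primary analysis, or that the primary method is undecided, and the documents do not support that. What remains is a sentence and a screening rule whose stated scope is too wide.

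A reader might also infer a competing primary test from the general rule in SAP 6.4 ("The comparison between the intervention versus placebo groups will be done using the chi-square test"), which goes on to the t-test or Mann-Whitney for quantitative variables. That inference is too strong as well. The same section then names a specific model for total days, and Table 4 has no such test. The t and Mann-Whitney P-values for absence days appear in Tables 2 and 3, for baseline and two-week follow-up items. The rule chooses one test by distribution and does not invite picking the best of several. It is still true that no sentence says how those P-values rank against the model.

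On (a), the reply is that the effect is small, that power is already about 90% or more in these scenarios, and that the documents give no sex effect. All of this stands. Nor does the omission bias the comparison or raise the false-positive rate, though a reader might suppose so. The case for adding sex is that it is already collected, already used in the other models, and costs one parameter.

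**Conclusion.** Both parts hold, at modest weight, and should be fixed.

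(a) Sex is missing from the primary model without a stated reason. The consequence is a reported standard error about 0.4% to 6% too large and roughly 0 to 4 points of power forgone, for assumed sex ratios of 1.25 to 2. If sex has little relation to absence, the effect is close to nil.

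(b) Read literally, SAP 6.1 contradicts Tables 4 and 5 on 7 of 15 endpoints, the primary among them. This rests on the text alone. It is over-broad drafting with a recoverable intent. The nights scale of the two intensive-care rows is a further, separate inconsistency.

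**What to change.** 1. Add sex to the negative binomial model in SAP Statistical analysis, SAP 6.4 and Protocol Statistical methods, and keep the other listed covariates. Reconcile the different list in the Protocol abstract. Because the interim rule uses this model, the change also alters the interim statistic, and the protocol text should say so.
2. In SAP 6.1, limit the log-rank/Cox sentence and the covariate screen to the eight cumulative-incidence rows of Table 5. Leave COVID-19 infection and death with the Poisson model of the Table 5 footnote. Correct the scale of the two intensive-care rows in Table 1 so that it matches Table 5.
3. State that the Table 4 negative binomial model is the single primary analysis of total days of unplanned absenteeism due to illness, and that any t-test or Mann-Whitney comparison of absence days is descriptive.

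The cost is a few sentences in the SAP, the matching protocol text and one extra model parameter. No new data are needed, and the sample size does not change.
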